2. LIST OF ABBREVIATIONS

Term	Definition / description
AE	Adverse Event
AESI	Adverse event of special interest
ALT	Alanine aminotransferase
AST	Aspartate aminotransferase
AUC _{0-∞}	Area under the concentration-time curve of the analyte in plasma over the time interval from 0 extrapolated to infinity
AUC _{0-tz}	Area under the concentration-time curve of the analyte in plasma over the time interval from 0 to the last quantifiable data point
BI	Boehringer Ingelheim
C _{max}	Maximum measured concentration of the analyte in plasma
COVID	Coronavirus disease
CTP	Clinical Trial Protocol
CTR	Clinical Trial Report
CV	Arithmetic coefficient of variation
ECG	Electrocardiogram
gCV	geometric coefficient of variation
gMean	Geometric mean
HR	Heart rate
ICH	International Conference On Harmonisation
IPD	Important protocol deviations
LLOQ	Lower limit of quantification
MedDRA	Medical Dictionary For Regulatory Activities
On-trt	On-treatment
PD	Pharmacodynamics
PK	Pharmacokinetics
PKS	Pharmacokinetic parameter analysis set
PR	Pulse rate
QRS complex	Combination of the Q, R, and S waves
QT interval	Time between start of the Q-wave and the end of the T-wave in an

Term	Definition / description
	electrocardiogram
QTcB	QT interval, heart rate corrected according to Bazetts formula
QTcF	QT interval, heart rate corrected according to Fridericias formula
RAGe	Report appendix generator
RPM	Report Planning Meeting
RR interval	ECG interval from the peak of the R wave to the peak of the subsequent R wave
SAE	Serious adverse event
SD	Standard Deviation
SOC	System Organ Class
TS	Treated set
TSAP	Trial Statistical Analysis Plan
ULN	Upper limit of normal range

3. INTRODUCTION

As per ICH E9 (1) the purpose of this document is to provide a more technical and detailed elaboration of the principal features of the analysis described in the revised CTP, and to include detailed procedures for executing the statistical analysis of the primary variables and other data.

This TSAP assumes familiarity with the CTP and its amendments. In particular, the TSAP is based on the planned analysis specification as written in CTP Section 7 "Statistical Methods and Determination of Sample Size". Therefore, TSAP readers may consult the revised CTP for more background information on the study, e.g., on study objectives, study design and population, treatments, definition of measurements and variables, planning of sample size, randomisation.

Study data will be stored in a trial database within Medidata Rave system.

The statistical analyses will be performed within the validated working environment CARE, including SASTM (current Version 9.4, by [REDACTED]), and a number of SASTM-based tools (e.g., macros for the analyses of AE data or laboratory data; Report Appendix Generator system (RAGe) for compilation/formatting of the CTR appendices).

PK parameters will be calculated using Phoenix WinNonlinTM software (version Phoenix 8.1, [REDACTED]).

4. CHANGES IN THE PLANNED ANALYSIS OF THE STUDY

Section 7.3.3 of the CTP states that “dose proportionality will be explored for the further pharmacokinetic endpoints specified in Section 2.2.2.2”. The analysis of dose proportionality is not reasonable for all 12 further PK endpoints specified in the CTP. Therefore, this TSAP specifies that this analysis of further PK endpoints will be conducted for further PK endpoint [REDACTED] of BI 1569912.

Section 7.5.1 of the CTP states that the “relationship between plasma concentrations and ECG endpoints will be investigated in an exploratory manner” in the 30 mg BI dose group. Against the background of the steep PK profile observed for this drug in this trial, it was decided that the time differences observed between plasma samples and ECG measurements were too big to be acceptable (partly due to study procedures with extensive measurements performed at time points). Plasma concentrations and ECG measurements would not relate with each other. It was decided not to perform this analysis in this trial.

All other analyses described in this TSAP are in accordance with the statistical methods described in the revised CTP.

5. ENDPOINTS

5.1 PRIMARY ENDPOINT

Primary endpoint in the SRD part is the percentage of subjects with treatment-emergent drug-related adverse events.

Primary endpoints in the BA/FE part are AUC_{0-tz} and C_{max} of BI 1569912 in plasma.

5.2 SECONDARY ENDPOINTS

5.2.1 Key secondary endpoints

Not applicable.

5.2.2 Secondary endpoints

Secondary endpoints are PK endpoints of analyte BI 1569912, as defined in **Section 2.1.3 of the CTP**:

SRD-Part:

- $AUC_{0-\infty}$ (area under the concentration-time curve of the analyte in plasma over the time interval from 0 extrapolated to infinity)
- C_{max} (maximum measured concentration of the analyte in plasma)

BA/FE-Part:

- $AUC_{0-\infty}$ (area under the concentration-time curve of the analyte in plasma over the time interval from 0 extrapolated to infinity)

5.3 FURTHER ENDPOINTS

5.3.1 Safety parameters

Safety and tolerability of BI 1569912 will be assessed based on further safety parameters defined in **Section 2.2.2.1 of the CTP**:

- *AEs (including clinically relevant findings from the physical examination)*
- *Safety laboratory tests*
- *12-lead ECG*
- *Continuous ECG monitoring (SRD-Part, only)*
- *Vital signs (blood pressure, pulse rate, respiratory rate, body temperature)*
- *Columbia-Suicide Severity Rating Scale (C-SSRS)*
- *Standardized physical/ neurological assessment [only as part of AE analysis]*
- *Assessment of dissociative symptoms ([...] CADSS)*
- *Electroencephalogram (EEG) [i.e., safety EEG, abnormal or normal]*

CADSS

CTP: *The CADSS is a clinician administered measure of perceptual, behavioural and attentional alterations during active dissociative experiences. The scale contains 23 subjective items, each rated from 0 (not at all) to 4 (extremely).*

The total score of the CADSS is the sum of the 23 item scores, ranging from 0 to 92. Statistical analysis of the CADSS will be based on the total score.

12-lead ECG endpoints

For the definition of baseline and a summary of time points please refer to [Section 6.7](#).

Quantitative ECG endpoints:

The following quantitative ECG endpoints will be determined for the ECG variables QTcF, QT, HR, PR, QRS, RR and QTcB derived as described in [Section 10.1](#):

- absolute values (per time point)
- changes from baseline (per time point)
- percent changes from baseline (per time point; for HR, PR, QRS)

Categorical ECG endpoints

[figure not shown]
The following categorical ECG endpoints will be determined based on the quantitative ECG endpoints.

[figure not shown]
- New onset (meaning that this or a higher category was not present at baseline) of maximum QTcF interval > 450 to 480 msec, > 480 to 500 msec, or > 500 msec on treatment. For assignment of a particular subject to one of the above categories, all time points on-treatment (refer to [Table 6.7: 4](#) and [Table 6.7: 5](#)) will be considered.
- Maximum change from baseline in QT interval of ≤ 60 msec, or > 60 msec on treatment
- Maximum change from baseline in QTcF interval of ≤ 30 msec, > 30 to ≤ 60 msec, or > 60 msec on treatment

The occurrence of any of the following in the 30 mg dose group (with semi-automatic measurement of RR and QT intervals) will be viewed as "notable findings". Notable findings will not be defined for any of the other treatments (with automatic measurements, exclusively).

- New onset (not present at baseline) of uncorrected QT interval > 500 msec at any time on treatment
- New onset of QTcF interval > 500 msec at any time on treatment
- Change from baseline of QTcF > 60 msec at any time on treatment
- Percent change from baseline of HR $\geq 25\%$, when corresponding on-treatment value of HR is > 100 beats/min, or percent change from baseline of HR $\leq -25\%$, when corresponding on-treatment value of HR is < 50 beats/min, at any time on treatment

For a detailed description of ‘new onset’, refer to [Section 10.3](#).

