#### Stopping Rules Related to Dose Groups:

- In case of any safety concerns, as listed below but not limited to them, the trial will be mandatorily discontinued. Occurrence of severe non-serious adverse events

considered as drug-related by the investigator in 2 subjects of the same dose group (8 subjects) in the SRD-Part, or 3 subjects of the BA/ FE group (12 subjects), or occurrence of at least one drug-related serious adverse event (SAE). Moreover, dose escalation in the SRD-Part will be terminated, if more than 3 of the actively dosed subjects at one dose level show drug-related and clinically relevant adverse events of at least moderate intensity.

- Clinical apparent seizures/ convulsions in one or more subjects in the same dose group.
- EEG changes consistent with pro-convulsive activities (e.g., spike and wave) that is considered to be drug-related in two or more subjects of the same dose group.
- Clinically relevant changes in the neurological assessment indicating dose-limiting intolerance that is considered to be drug-related in one or more subjects of the same dose group.
- Dose escalation in the SRD-Part or treatment in the BA/ FE-Part will be stopped, if at least 2 subjects on active treatment at one dose level (SRD-Part) or 2 subjects in the BA/ FE-Part have relevant individual QT prolongations, i.e., a QTc increase of greater than 60 ms from baseline and/ or an absolute QT or QTc greater than 500 ms, as confirmed by a repeat ECG recording.
- Dose escalation in the SRD-Part will be stopped, if the  $C_{\max}$  or  $AUC_{0-24h}$  of at least 1 subject of one dose group increases above the following exposure thresholds or if the estimated geometric mean exposure is expected to exceed a  $C_{\max}$  of 1560 nM or an  $AUC_{0-24h}$  of 2490 nM\*h. In this case, one or two additional dose levels lower than the planned next dose level may be given, as long as the expected geometric mean exposure values of the interim dose do not exceed these exposure thresholds. Estimation will be done based on preliminary pharmacokinetic results of preceding dose groups (see Section [7.4](#))

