17. Blood donation of more than 100 mL within 30 days of planned administration of trial medication or intended blood donation during the trial
18. Sperm donation from the time of drug administration until 30 days thereafter
19. Intention to perform excessive physical activities within one week prior to the administration of trial medication or during the trial
20. Inability to comply with the dietary regimen of the trial site
21. A marked baseline prolongation of QT/ QTc interval (such as QTc intervals that are repeatedly greater than 450 ms) or any other relevant ECG finding at screening
22. A history of additional risk factors for Torsade de Pointes (such as heart failure, hypokalaemia, or family history of Long QT Syndrome)
23. Subject is assessed as unsuitable for inclusion by the investigator, for instance, because the subject is not considered able to understand and comply with study requirements, or has a condition that would not allow safe participation in the study, or is in custody by order of an authority or court of law

In addition, the following trial-specific exclusion criteria apply:

24. Any lifetime history of suicidal behaviour (i.e. actual attempt, interrupted attempt, aborted attempt, or preparatory acts or behaviour)
25. Any suicidal ideation of type 2 to 5 on the C-SSRS (i.e. active suicidal thought, active suicidal thought with method, active suicidal thought with intent but without specific plan, or active suicidal thought with plan and intent) in the past year prior to randomization

26. History or presence of epilepsy, history of more than one febrile seizure in childhood or a family history of seizures/ convulsions
27. Epileptiform abnormalities in EEG at Screening
28. History of clinically relevant head injury or trauma (e.g., associated with loss of consciousness)

In addition, the following SARS-CoV-2/COVID-19-specific exclusion criteria apply:

29. A positive PCR test for SARS-CoV-2/COVID-19 and/ or any clinical symptom suggestive for this disease at screening and on Day -3.

For study restrictions, refer to Section [4.2.2](#).

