| Title of protocol   |  | Safety, tolerability, pharmacokinetics and pharmacodynamics of single rising oral doses of BI 1569912 in healthy male subjects (single-blind, partially randomized within dose groups, placebo-controlled, parallel-group design) with an additional relative bioavailability/ food effect part (open-label, randomized, three-way crossover design) |
| To be implemented only after approval of the IRB/ IEC/ Competent Authorities  |  |   |
| To be implemented immediately in order to eliminate hazard – IRB/ IEC/ Competent Authority to be notified of change with request for approval |  |    |
| Can be implemented without IRB/ IEC/ Competent Authority approval as changes involve logistical or administrative aspects only                |  |    |
| Section to be changed   |  | Flow Chart – SRD part;

Flow Chart – BA/ FE part;

Section 5.2.6.4;

Section 5.3.1;

Throughout the document.  |
| Description of change   |  | Insertion of the 0:05 (08:15) PK sampling time point
Shift of the 2:15 (10:15) PK sampling time point to 2:30 (10:30)
Deletion of the 10:00 (18:00) PK sampling time point;

Insertion of Footnote 15 (Sampling times and periods may be adapted based on information obtained during the trial ...);                                    |

|                             |  |  |
|-----------------------------|--|--|
|                             |  | 
Description of the adjudication process at [REDACTED], if two readers have deviating opinions on EEGs; inclusion of outcome categories ('normal', 'abnormal/ epileptiform', 'abnormal/ non-epileptiform');
 
BA/FE-part: Permission of flexibility concerning PK sampling time points and -periods based on information obtained during the course of the trial;
 
Minor editorial and formatting changes for consistency reasons.
   |

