7. PLANNED ANALYSIS

The format of the listings and tables will follow the BI guideline "Reporting of clinical trials and project summaries" ([6](#)).

The individual values of all subjects will be listed. Listings will be sorted by treatment or sequence group, subject number and visit (if visit is applicable in the respective listing). AE listings will be sorted by assigned treatment (see [Section 7.8.1](#) below for details). The listings will be contained in Appendix 16.2 (SDL) of the CTR.

The following standard descriptive statistical parameters will be displayed in summary tables of continuous variables:

N	number of non-missing observations
Mean	arithmetic mean
SD	standard deviation
Min	minimum
Median	median
Max	maximum

For plasma concentrations as well as for all PK parameters the following descriptive statistics will additionally be calculated:

CV	arithmetic coefficient of variation
gMean	geometric mean
gCV	geometric coefficient of variation

For PK parameters the following descriptive statistics will additionally be calculated:

P10	10 th percentile
Q1	1 st quartile
Q3	3 rd quartile
P90	90 th percentile

The data format for descriptive statistics of plasma concentrations will be identical with the data format of the respective concentrations. The descriptive statistics of PK parameters will be calculated using the individual values with the number of decimal places as provided by the evaluation program. Then the individual values as well as the descriptive statistics will be reported with three significant digits in the CTR.

Tabulations of frequencies for categorical data will include all possible CRF categories and will display the number of observations in a category as well as the percentage (%) relative to the respective treatment group. Percentages will be rounded to one decimal place. The category missing will be displayed if and only if there actually are missing values. Percentages will be based on all subjects in the respective subject set whether they have non-missing values or not.

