7.8.5.5 Assessment of safety electroencephalogram (EEG)

Abnormal findings will be reported as baseline conditions (at screening) or AEs (during the trial), if judged clinically relevant by the investigator.

Frequency of subjects categorized by EEG abnormalities will be presented by treatment and day.

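### The safety EEG is defined in the SAP with two levels only, so the planned summary does not show epileptiform findings by dose

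*SAP*

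**What the plan says.** The SAP specifies the safety EEG in these places:

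- **SAP 5.3.1** lists the endpoint as "Electroencephalogram (EEG) [i.e., safety EEG, abnormal or normal". This is the SAP's only explicit statement of EEG levels.
- **SAP 7.8.5.5** plans one summary: "Frequency of subjects categorized by EEG abnormalities will be presented by treatment and day". On individual findings it says: "Abnormal findings will be reported as baseline conditions (at screening) or AEs (during the trial), if judged clinically relevant by the investigator".
- **SAP 6.1** names the safety EEG among the data analysed by treatment with baseline kept apart from post-baseline. **SAP 6.7** defines baseline as the last off-treatment value before the dose, separately for each treatment of the BA/FE part.
- **SAP 7** adds two general rules: "Tabulations of frequencies for categorical data will include all possible CRF categories" and "The individual values of all subjects will be listed".

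The protocol separates epileptiform findings from other EEG abnormalities:

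- **Sections 1.4.7 and 5.7** give the purpose of the repeated EEGs as detecting pro-convulsive activity, because of the seizures and convulsions in dogs.
- **Exclusion criterion 27** (3.3.3) bars "Epileptiform abnormalities in EEG at Screening" and no other kind of EEG abnormality.
- **The dose-group stopping rule** (1.4.7) concerns "EEG changes consistent with pro-convulsive activities (e.g., spike and wave) that is considered to be drug-related in two or more subjects".
- **The Amendment 6 log** (11.6) records the "inclusion of outcome categories ('normal', 'abnormal/ epileptiform', 'abnormal" and, as the third category, abnormal but non-epileptiform.

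**The concern.** The protocol's EEG question is whether the drug provokes epileptiform activity, and at which dose. A two-level endpoint puts a post-dose spike-and-wave pattern and mild non-epileptiform slowing in the same cell. A non-epileptiform abnormality that the investigator does not consider clinically relevant is compatible with entry, so some abnormal readings may have nothing to do with treatment. With six active subjects per dose group, one such reading changes the displayed rate by 16.7 percentage points. An epileptiform signal could be hidden among harmless findings, or harmless findings could look like a signal.

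The SAP is more careful elsewhere. It defines new-onset categories for QTcF (5.3.1) and baseline-to-last-value frequency tables for laboratory data (7.8.2). The EEG, included because of the seizure findings in dogs, has no corresponding rule.

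**Working it through.** The documents give no EEG rate, power or sample-size figure, so there is nothing to reproduce. The check is mainly a reading of the text.

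**1. Levels against purpose.** SAP 5.3.1 has two levels. The protocol's purpose, entry criterion, stopping rule and reader categories each single out epileptiform or pro-convulsive findings. The two-level definition therefore merges the two abnormal categories that the readers keep apart.

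**2. Can a non-epileptiform abnormality be present at entry?** Criterion 27 removes only epileptiform findings. Criterion 1 removes findings judged clinically relevant, and criteria 7, 26 and 28 remove CNS disease, seizure history and relevant head injury. What remains possible at entry is a non-epileptiform abnormality not judged clinically relevant.

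**3. What the two-level table shows.** Three hypothetical active groups of six:

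| Group | Event in one subject | Abnormal at baseline | Abnormal post-dose | Epileptiform post-dose |
|---|---|---|---|---|
| A | normal, then epileptiform | 0/6 | 1/6 (16.7%) | 1/6 |
| B | normal, then non-epileptiform | 0/6 | 1/6 (16.7%) | 0/6 |
| C | non-epileptiform, then epileptiform | 1/6 | 1/6 (16.7%) | 1/6 |

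A and B have the same two-level entries but answer the question differently. In C the two-level counts do not change at all, although baseline and post-dose are shown separately. Separating baseline helps, but it does not replace the missing category.

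**4. By day.** Both flow charts schedule four post-dose EEGs on Day 1 (0:45, 1:15, 3:00 and 8:00 h), then one each at 24, 48 and 72 h. SAP 7.8.5.5 does not say how the four Day 1 readings become one daily result. Timing matters: in the dog dose-range study, focal seizures began about 15 min post-dose, and generalised convulsions came at about 24 to 28 h (protocol 1.2.3.2).

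**5. Illustration of background.** Let p be the proportion of subjects with a non-epileptiform abnormal EEG and no drug effect. This is an assumption, shown over a range. Six active subjects per group is from protocol 3.1. SAP 6.1 lists seven SRD doses, so the pooled placebo group is 7 × 2 = 14 as planned. Assuming independent subjects, P(at least one abnormal among n) = 1 − (1 − p)^n.

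| p (assumed) | n = 6 (one active group) | n = 14 (pooled placebo) |
|---|---|---|
| 2% | 11.4% | 24.6% |
| 5% | 26.5% | 51.2% |
| 10% | 46.9% | 77.1% |
| 20% | 73.8% | 95.6% |

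For example, at p = 5%: 1 − 0.95^6 = 1 − 0.735 = 0.265. At any of these rates, a single abnormal EEG in a dose group says little about epileptiform activity. Pooled placebo would show some of this background, but it cannot say which kind of abnormality an active subject had.

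**The case against.** The strongest reply is that the SAP may already produce three rows. The bracket in 5.3.1 may serve only to distinguish the safety reading from quantitative EEG. The operative sentence in 7.8.5.5 does not fix two levels, and SAP 7 requires every CRF category to appear. If the CRF holds the three reader categories, the table would show them. This cannot be excluded: the public copy does not show protocol 5.2.6.4, the CRF or SAP Section 10. But the only levels the SAP states are two, and a reader should not need the CRF to learn what a safety endpoint is. If three are intended, one sentence settles it.

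A second reply is that nothing is lost. Individual values are listed, and clinically relevant findings become adverse events, which are tabulated by preferred term. This stands in part. Listings give no incidence by dose, and the adverse-event route depends on a judgement of clinical relevance by investigators who know the treatment (protocol 4.1.5.1).

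Three stronger readings are tempting, and the documents do not support them:

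- **That the SAP ignores baseline.** SAP 6.1 names the safety EEG and 6.7 defines its baseline. What is missing is a within-subject new-onset rule.
- **That a subject abnormal at entry counts as abnormal on every post-dose day.** No document says that such findings persist.
- **That the two-level count could trigger or mask the stopping rule.** The rule needs drug-related, pro-convulsive changes, and this table does not operate it. Escalation relies on EEG reports reviewed during the trial (protocol 3.1), so background probabilities should not be compared with the rule's count.

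**Conclusion.** The point holds as a defect in the pre-specified summary. As defined, it pools epileptiform with non-epileptiform abnormalities, has no new-onset count, and so does not show epileptiform incidence by dose. It does not show that data are lost or that subjects were monitored inadequately.

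The firm size is that one subject is 16.7% of an active group, whichever abnormality he has. The 26% to 47% chance of at least one background abnormality among six rests on an assumed 5% to 10% rate (11% to 74% over 2% to 20%), which the documents do not give. Baseline and pooled placebo counts would reveal part of that background.

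The conclusion assumes that the two-level definition in 5.3.1 governs the table. The Amendment 6 log is used only as evidence that the three categories exist. The change is worth making because it is cheap and concerns the finding for which the EEG was included.

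**What to change.** In SAP 5.3.1 and 7.8.5.5:

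1. Replace the two-level definition with the three reader categories: normal, abnormal/epileptiform and abnormal/non-epileptiform.
2. Tabulate them by treatment and planned time. If a daily summary is kept, state how several readings on one day are combined.
3. Add the number of subjects per treatment with a post-dose epileptiform finding that was absent at the baseline EEG of that period.
4. Optionally, add a shift table from baseline category to worst post-dose category.

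The cost is SAP wording and one table, or two with the shift table. Day -1 EEGs are already scheduled in both parts, and no new assessment is needed. One check comes first: that the database holds the three categories for all dose groups, including those read before Amendment 6. The log describes the reporting process as already established, which suggests that it does.
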